6. EXPECTED TOXICITIES AND DOSING DELAYS/DOSE MODIFICATIONS

If possible, symptoms will be managed symptomatically. In the case of toxicity, appropriate medical treatment will be used (including anti-emetics, anti-diarrheals, etc.).

All adverse events experienced by participants will be collected from the time of the first dose of study treatment, through the study and until the final study visit. Participants continuing to experience toxicity at the off study visit may be contacted for additional assessments until the toxicity has resolved or is deemed irreversible.

6.1 Anticipated Toxicities

All drugs in this study have been in routine clinical use for many years, and are associated with rare adverse effects. Additional radiation exposure is less than the yearly natural background radiation in the US. A list of the adverse events and potential risks associated with the drugs administered in this study appear below and will determine whether dose delays and modifications will be made or whether the event requires expedited reporting **in addition** to routine reporting.

CONFIDENTIAL

This document is confidential. Do not disclose or use except as authorized.

6.1.1 *Adverse Event List for Tetracycline*

Significant Adverse Reactions (Rare):

- Cardiovascular: Pericarditis
- Central nervous system: Bulging fontanel in infants, increased intracranial pressure, paresthesia, pseudotumor cerebri
- Dermatologic: Exfoliative dermatitis, photosensitivity, pigmentation of nails, pruritus
- Gastrointestinal: Abdominal cramps, anorexia, antibiotic-associated pseudomembranous colitis, diarrhea, discoloration of teeth and enamel hypoplasia (young children), esophagitis, nausea, pancreatitis, staphylococcal enterocolitis, vomiting
- Hematologic: Thrombophlebitis
- Hepatic: Hepatotoxicity
- Renal: Acute renal failure, azotemia, renal damage
- Miscellaneous: Anaphylaxis, candidal superinfection, hypersensitivity reactions, superinfection

Contraindications: Hypersensitivity to demeclocycline, tetracyclines, or any component of the formulation

Concerns related to adverse effects:

- Increased blood urea nitrogen (BUN): May be associated with increases in BUN secondary to antianabolic effects; use caution in patients with renal impairment.
- Photosensitivity: May cause photosensitivity; discontinue if skin erythema occurs. Use skin protection and avoid prolonged exposure to sunlight; do not use tanning equipment.
- Pseudotumor cerebri: Has been (rarely) reported with tetracycline use; usually resolves with discontinuation.
- Superinfection: Prolonged use may result in fungal or bacterial superinfection, including *C. difficile*-associated diarrhea (CDAD) and pseudomembranous colitis; CDAD has been observed >2 months postantibiotic treatment.

Disease-related concerns:

- Hepatic impairment: Use with caution in patients with hepatic impairment; dose adjustment and/or adjustment to interval frequency recommended. Hepatotoxicity and hepatic failure have been reported rarely with use.
- Renal impairment: Use with caution in patients with renal impairment; dosage adjustment recommended. Nephrotoxicity has also been reported with use, particularly in the setting of cirrhosis.

Special populations:

Pediatrics: May cause tissue hyperpigmentation, enamel hypoplasia, or permanent tooth discoloration; use of tetracyclines should be avoided during tooth development (children <8 years of age) unless other drugs are not likely to be effective or are contraindicated.

Pregnancy: Do not use during pregnancy or nursing. In addition to affecting tooth development, tetracycline use has been associated with retardation of skeletal development and reduced bone growth

CONFIDENTIAL

This document is confidential. Do not disclose or use except as authorized.

6.1.2 *Adverse Event List for Demeclocycline*

Significant Adverse Reactions (Rare):

- Cardiovascular: Pericarditis
- Central nervous system: Bulging fontanel (infants), dizziness, headache, pseudotumor cerebri (adults)
- Dermatologic: Angioedema, anogenital inflammatory lesions (with monilial overgrowth), erythema multiforme, erythematous rash, exfoliative dermatitis (rare), maculopapular rash, photosensitivity, pigmentation of skin, Stevens-Johnson syndrome (rare), urticaria
- Endocrine & metabolic: Microscopic discoloration of thyroid gland (brown/black), nephrogenic diabetes insipidus, thyroid dysfunction (rare)
- Gastrointestinal: Anorexia, diarrhea, dysphagia, enterocolitis, esophageal ulcerations, glossitis, nausea, pancreatitis, vomiting
- Genitourinary: Balanitis
- Hematologic: Eosinophilia, neutropenia, hemolytic anemia, thrombocytopenia
- Hepatic: Hepatitis (rare), hepatotoxicity (rare), liver enzymes increased, liver failure (rare)
- Neuromuscular & skeletal: Myasthenic syndrome, polyarthralgia, tooth discoloration (children <8 years, rarely in adults)
- Ocular: Visual disturbances
- Otic: Tinnitus
- Renal: Acute renal failure, BUN increased
- Respiratory: Pulmonary infiltrates
- Miscellaneous: Anaphylaxis, anaphylactoid purpura, fixed drug eruptions (rare), lupus-like syndrome, superinfection, systemic lupus erythematosus exacerbation

Contraindications: Hypersensitivity to demeclocycline, tetracyclines, or any component of the formulation

Concerns related to adverse effects:

- Diabetes insipidus syndrome: Dose-dependent nephrogenic diabetes insipidus is common with use; however, this adverse event of demeclocycline has been used as a therapeutic advantage in the off-label use of hyponatremia associated with SIADH.
- Increased BUN: May be associated with increases in BUN secondary to antianabolic effects; use caution in patients with renal impairment.
- Photosensitivity: May cause photosensitivity; discontinue if skin erythema occurs. Use skin protection and avoid prolonged exposure to sunlight; do not use tanning equipment.
- Pseudotumor cerebri: Has been (rarely) reported with tetracycline use; usually resolves with discontinuation.
- Superinfection: Prolonged use may result in fungal or bacterial superinfection, including *C. difficile*-associated diarrhea (CDAD) and pseudomembranous colitis; CDAD has been observed >2 months postantibiotic treatment.

Disease-related concerns:

- Hepatic impairment: Use with caution in patients with hepatic impairment; dose adjustment and/or adjustment to interval frequency recommended. Hepatotoxicity and hepatic failure have been reported rarely with use.
- Renal impairment: Use with caution in patients with renal impairment; dosage adjustment recommended. Nephrotoxicity has also been reported with use, particularly in the setting of cirrhosis.

CONFIDENTIAL

This document is confidential. Do not disclose or use except as authorized.

Special populations:

Pediatrics: May cause tissue hyperpigmentation, enamel hypoplasia, or permanent tooth discoloration; use of tetracyclines should be avoided during tooth development (children <8 years of age) unless other drugs are not likely to be effective or are contraindicated.

Pregnancy: Do not use during pregnancy. In addition to affecting tooth development, tetracycline use has been associated with retardation of skeletal development and reduced bone growth

6.1.3 *Radiation Exposure Risks*

Will perform a volumetric dual energy CT of L1, L2, and S1 using a second-generation dual-source 128-row multi-detector CT scanner (Somatom Definition Flash; Siemens Medical Solutions, Forchheim, Germany). Subjects will be positioned on a quantitative CTPRO calibration phantom (Mindways Software). Helical scans will be performed at 80 and 140 kV by using 210 and 80 mAs, respectively. Other scanning parameters included 1-second gantry rotation time, 0.9:1 pitch, and 64 x 0.6-mm detector configuration with double z-sampling. The images will be reconstructed at 2-mm section thickness and 2-mm section interval by using the I31f reconstruction kernel with a sinogram-affirmed iterative reconstruction (SAFIRE; Siemens Healthcare) setting of 2. The effective dose for each DECT scan is about 2 mSv. For 2 scans, the total effective dose is about 4 mSv which is about the annual background radiation dose.

6.2 **Toxicity Management**

6.2.1 *Management of Tetracycline Toxicity*

Renal / Hepatic Impairment: Tetracycline will not be administered to patients with pre-existing renal or hepatic impairment.

Photosensitivity: Patients will be advised to use skin protection while taking tetracycline. In addition, patients will be advised against prolonged exposure to sunlight and use of tanning equipment. If skin erythema occurs, patients will be advised to discontinue taking the drug and contact the study team.

Superinfection: Patients will be informed of this risk, and will be closely monitored for any GI symptoms. Patients will be advised to discontinue taking the drug and contact their primary care provider and the study team, if any symptoms of infection occur.

Pseudotumor: Patients will be advised to discontinue taking the drug and contact the study team if headache, photophobia, gait disturbances, or any other neurological deficits occur.

Special populations: pregnant and lactating women and children will be excluded from the study due to the concerns related to tetracycline use in these populations (outlined in Section 6.1.1 Adverse Effects of Tetracycline 6.1.2).

CONFIDENTIAL

This document is confidential. Do not disclose or use except as authorized.

6.2.2 *Management of Demeclocycline Toxicity*

Diabetes Insipidus: Patients will be advised to discontinue taking demeclocycline and contact their PCP and the study team, if they experience excessive thirst, urination, headache, dizziness, nausea/vomiting, or any other concerning symptoms.

Renal / Hepatic Impairment: Demeclocycline will not be administered to patients with pre-existing renal or hepatic impairment.

Photosensitivity: Patients will be advised to use skin protection while taking demeclocycline. In addition, patients will be advised against prolonged exposure to sunlight and use of tanning equipment. If skin erythema occurs, patients will be advised to discontinue taking the drug and contact the study team.

Superinfection: Patients will be informed of this risk, and will be closely monitored for any GI symptoms. Patients will be advised to discontinue taking the drug and contact their primary care provider and the PI study team, if any symptoms of infection occur.

Pseudotumor: Patients will be advised to discontinue taking the drug and contact the study team if headache, photophobia, gait disturbances, or any other neurological deficits occur.

Special populations: pregnant and lactating women and children will be excluded from the study due to the concerns related to tetracycline use in these populations (outlined in Section 6.1.2 Adverse Effects of Demeclocycline 6.1.2).

6.2.3 *Management of Radiation Toxicity*

Additional radiation dose is approximately 4 mSv. This amount of radiation is less than the yearly natural background radiation in the US. We do not anticipate any toxic effects of this dose of radiation to the patients. However, patients will be advised that radiation is a potential teratogen. For this reason, women of child-bearing potential and men must agree to use adequate contraception (hormonal or barrier method of birth control; abstinence) prior to study entry and for the duration of study participation. Should a woman become pregnant or suspect she is pregnant while participating in this study, she should inform her treating physician immediately.

6.3 **Dose Modifications/Delays**

N/A

CONFIDENTIAL

[figure not shown]
This document is confidential. Do not disclose or use except as authorized.

7. DRUG FORMULATION AND ADMINISTRATION

7.1 Tetracycline

7.1.1 Description

The chemical name is: (4*S*,6*S*,12*aS*)-4-(dimethylamino)-1,4,4*a*,5,5*a*,6,11,12*a*-octahydro-3,6,10,12,12*a*-pentahydroxy-6-methyl-1,11-dioxonaphthacene-2-carboxamide. The molecular formula is $C_{22}H_{24}N_2O_8$. The Molecular weight is 444.435 g/mol

Tetracycline

Bioavailability: 60–80%
Metabolism: Not Metabolized
Half-life: 6-11 hours
Excretion: Renal and Fecal

7.1.2 Form

Capsule, oral, as hydrochloride: 250 mg, 500 mg

7.1.3 Storage and Stability

All pharmaceuticals will be stored at the Massachusetts General Hospital Oncology Clinical Trials Pharmacy (Yawkey-7).

7.1.4 Compatibility

N/A

7.1.5 Handling

Qualified personnel, familiar with procedures that minimize undue exposure to themselves and the environment, should undertake the preparation, handling, and safe disposal of the antimicrobial drug in a self-contained and protective environment.

7.1.6 Availability

All pharmaceuticals used in this study will be obtained from the in-patient pharmacy at MGH. Dispense of the bone labeling drugs will happen during the last day of the radiotherapy. This will be approximately 4 days prior to the start of the labeling cycle. The total amount of pills for the labelset (24 tablets) will be divided over 2 bottles, each containing 12 pills. The bottles will be labeled 'Period 1' and 'Period 2', indicating one of the 3 day periods during which the pills are self-administered.

CONFIDENTIAL

This document is confidential. Do not disclose or use except as authorized.

7.1.7 *Preparation*

All pharmaceuticals will be prepared at the Massachusetts General Hospital Clinical Trials Pharmacy. The bone labeling drugs will be divided in 2 bottles with 12 tablets per bottle. One bottle will contain the exact amount of pills that will be self-administered during one of the 3 day period. There will be 2 of these 3 day periods.

7.1.8 *Administration*

Participants in the surgical arm will self-administer tetracycline 250mg PO QID (daily dose 1000 mg) during 2 periods of 3 days with a 12 day interval, i.e. days 24, 23 and 22 and days 9, 8 and 7 prior to the 1st stage of their scheduled surgery. Tetracycline should be administered on an empty stomach (ie, 1 hour prior to, or 2 hours after meals) to increase total absorption. Patients will be asked not to take aluminum containing antacids two hours before and after the medication has been given as it can interfere with bone binding. Patients will be instructed to take the bone labeling drug no more than 3 consecutive days.

7.1.9 *Ordering*

All pharmaceuticals will be ordered through the Massachusetts General Hospital Clinical Trials Pharmacy. The designated pharmacist for this study is [name] at [contact].

7.1.10 *Accountability*

The investigator, or a responsible party designated by the investigator, must maintain a careful record of the inventory and disposition of the bone labeling drugs (investigational or free of charge) using the NCI Drug Accountability Record or another comparable drug accountability form

7.1.11 *Destruction and Return*

At the end of the study, unused supplies of tetracycline and demeclocycline will be disposed of according to institutional policies. Destruction will be documented in the Drug Accountability Record Form.

[figure not shown]
7.2 **Demeclocycline (Declomycin)**

7.2.1 *Description*

The chemical name is: 2*E*,4*S*,4*aS*,5*aS*,6*S*,12*aS*)-2-[amino(hydroxy)methylidene]-7-chloro-4-(dimethylamino)-6,10,11,12*a*-tetrahydroxy-1,2,3,4,4*a*,5,5*a*,6,12,12*a*-decahydrotetracene-1,3,12-trione. The molecular formula is C₂₁H₂₁ClN₂O₈ The Molecular weight is 464.853 g/mol

CONFIDENTIAL

This document is confidential. Do not disclose or use except as authorized.

Demeclocycline

Bioavailability: 60–80%
Protein binding: 41–50%
Metabolism: Hepatic
Half-life: 10–17 hours
Excretion: Renal

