2.3 Bone Labeling Drugs

2.3.1 *Tetracycline*

Tetracycline is an FDA-approved anti-microbial drug, available in the US in generic form. It has minimal, well-documented adverse effects. Tetracycline can be safely self-administered by the patient in a form of oral pill on outpatient basis. In this study, it will be used as a fluorescent label for dynamic bone histomorphometry studies, in accordance with a well-established protocol. Manufacturer: Varies

2.3.2 *Demeclocycline (Declomycin)*

Demeclocycline is an FDA-approved anti-microbial drug, available in the US in generic form. It is a tetracycline derivative, and has a similar safety profile. All associated adverse effects are minimal and well-documented. Demeclocycline can be safely self-administered by the patient in a form of oral pill on outpatient basis. In this study, it will be used as an accessory fluorescent label (in addition to tetracycline) for dynamic histomorphometry studies, in accordance with a well-established protocol. Manufacturer: Varies

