5.2 Bone Labeling Drug Administration

For participants in the non-surgical arm, no bone labeling drugs are administered. These participants will receive a standard radiation regimen with blood samples and imaging (QCT) only as their participation in this study. For participants in the surgical arm, the bone labeling drugs are described below.

5.2.1 *Demeclocycline*

Participants in the surgical arm will self-administer the first label set; demeclocycline 150 mg PO QID (daily dose 600 mg) during 2 periods of 3 days, starting day 18 and day 3 prior to the start of their scheduled pre-operative radiotherapy. Participants will be given a drug diary (Appendix 1) to keep a record of the dosing. Demeclocycline comes in a form of an oral pill and does not require any special equipment for administration. It has a well-established safety profile with minimal adverse effects. No observation period or vital signs monitoring is required. Demeclocycline should be administered 1 hour before or 2 hours after food or milk, with adequate amounts of fluid to decrease the risk of esophageal irritation and ulceration. If a dose is vomited, the participant should contact the research coordinator, so we can provide an extra dose. Contact information will be provided in the drug diary.

5.2.2 *Tetracycline*

Participants in the surgical arm will also self-administer the second label set; tetracycline 250mg PO QID (daily dose 1000 mg) during 2 periods of 3 days, starting day 24 and day 9 prior to their scheduled surgery. Participants will be given a drug diary (Appendix 1) to keep a record of the dosing. Tetracycline comes in a form of an oral capsule and does not require any special equipment for administration. It has a well-established safety profile with minimal adverse effects. No observation period or vital signs monitoring is required. Tetracycline should be administered on an empty stomach: 1 hour prior to meals, or 2 hours after meals. If a dose is vomited, the participant should contact the research coordinator, so we can provide an extra dose. Contact information will be provided in the drug diary.

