7.2.7 Preparation

All pharmaceuticals will be prepared at the Massachusetts General Hospital Clinical Trials Pharmacy. The bone labeling drugs will be divided in 2 bottles with 12 tablets per bottle. One bottle will contain the exact amount of pills that will be self-administered during one of the 3 day period. There will be 2 of these 3 day periods..

CONFIDENTIAL

This document is confidential. Do not disclose or use except as authorized.

7.2.8 *Administration*

Participants in the surgical arm will self-administer demeclocycline 150 mg PO QID (daily dose 600 mg) during 2 periods of 3 days with a 12 day interval, i.e. day 18, 17 and 16 and day 3, 2 and 1 day prior to the start of their scheduled radiotherapy. Demeclocycline will be administered 1 hour before or 2 hours after food or milk. Administer with adequate amounts of fluid to decrease the risk of esophageal irritation and ulceration. Patients will be instructed to take the bone labeling drugs no more than 3 consecutive days.

7.2.9 *Ordering*

All pharmaceuticals will be ordered through the Massachusetts General Hospital Clinical Trials Pharmacy. The designated pharmacist for this study is [name] at [contact]

7.2.10 *Accountability*

The investigator, or a responsible party designated by the investigator, must maintain a careful record of the inventory and disposition of the bone labeling drugs (investigational or free of charge) using the NCI Drug Accountability Record or another comparable drug accountability form.

7.2.11 *Destruction and Return*

At the end of the study, unused supplies of tetracycline and demeclocycline will be disposed of according to institutional policies. Destruction will be documented in the Drug Accountability Record Form.

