17.2 Appendix 2: Patient Drug Schedule And Diary

Study Drug Schedule

CYCLE 1

	Days before start radiotherapy	18	17	16	15	14	13	12	11	10	9	8	7	6	5	4	3	2	1	Start radiotherapy
	Calendar Date	/	/	/													/	/	/	/
Time of Day to take Drug	Morning	Demeclocycline (150mg)	Demeclocycline (150mg)	Demeclocycline (150mg)													Demeclocycline (150mg)	Demeclocycline (150mg)	Demeclocycline (150mg)	
	Noon	Demeclocycline (150mg)	Demeclocycline (150mg)	Demeclocycline (150mg)													Demeclocycline (150mg)	Demeclocycline (150mg)	Demeclocycline (150mg)	
	Late afternoon	Demeclocycline (150mg)	Demeclocycline (150mg)	Demeclocycline (150mg)													Demeclocycline (150mg)	Demeclocycline (150mg)	Demeclocycline (150mg)	
	Night	Demeclocycline (150mg)	Demeclocycline (150mg)	Demeclocycline (150mg)													Demeclocycline (150mg)	Demeclocycline (150mg)	Demeclocycline (150mg)	

STUDY DRUG INSTRUCTIONS:

Study Drug: Demeclocycline

How Much: Your dose is 150 mg.

How Often: You will take each dose 4 times per day for 3 days.

When: You should take your dose 1 hour before or 2 hours after food or milk. You should take the dose with an adequate amount of fluids to reduce throat irritation. If a dose is vomited, please contact the research coordinator.

Contact information Research coordinator:

[name]

e-mail: [contact]

[contact]

Study Drug Schedule

CYCLE 2

	Days before FIRST Surgery	24	23	22	21	20	19	18	17	16	15	14	13	12	11	10	9	8	7	6	5	4	3	2	1	First Surgery	
	Calendar Date	/	/	/													/	/	/							/	
Time of Day to take Drug	Morning	Tetracycline (250mg)	Tetracycline (250mg)	Tetracycline (250mg)													Tetracycline (250mg)	Tetracycline (250mg)	Tetracycline (250mg)								
	Noon	Tetracycline (250mg)	Tetracycline (250mg)	Tetracycline (250mg)													Tetracycline (250mg)	Tetracycline (250mg)	Tetracycline (250mg)								
	Late afternoon	Tetracycline (250mg)	Tetracycline (250mg)	Tetracycline (250mg)													Tetracycline (250mg)	Tetracycline (250mg)	Tetracycline (250mg)								
	Night	Tetracycline (250mg)	Tetracycline (250mg)	Tetracycline (250mg)													Tetracycline (250mg)	Tetracycline (250mg)	Tetracycline (250mg)								

STUDY DRUG INSTRUCTIONS:

Study Drug: Tetracycline

How Much: Your dose is 250 mg.

How Often: You will take each dose 4 times per day for 3 days.

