When: You should take your dose on an empty stomach and either 1 hour before meals or 2 hours after meals. Please do not take aluminum containing antacids 2 hours before or after taking the dose. If a dose is vomited, please contact the research coordinator.

Contact information Research coordinator:

[name]

e-mail: [contact]

[contact]

CONFIDENTIAL

This document is confidential. Do not disclose or use except as authorized.

Effect of High Doses of Radiation on Bone Structure and Metabolism
 October, 5, 2016

OTHER MEDICATIONS TAKEN				Study Participant Self-Administration Study Drug Diary Cycle 1 Dana-Farber/Harvard Cancer Center			
If you take a daily medication (prescribed or otherwise), please use one line per drug and indicate the start and stop dates under the "Date(s) Taken" section (i.e., 6/2/09 - 6/5/09).				Participant Identifier: _____ Protocol #: 14-208 Your MD _____ Phone _____ Your RN _____ Phone _____			
Drug Name	Dose	Dates Taken	Reason Taken	STUDY DRUG INSTRUCTIONS:			
				Study Drug Cycle 1: Demeclocycline			
				How Much: Your dose is 150 mg How Often: You will take each dose 4 times per day for 3 days. When: You should take your dose 1 hour before or 2 hours after food or milk.			
				SPECIAL INSTRUCTIONS:			
				Please take your dose 1 hour before or 2 hours after food or milk. Please take the drug with a glass of water Please do not take the drugs for more than 3 consecutive days Please bring any unused study drug, all empty containers, and diary to the next clinic visit. If a dose is vomited, please contact the research coordinator.			
				Contact information Research coordinator: [name] e-mail: [contact] [contact]			
Study Participant Initials _____ Date _____							
FOR STUDY TEAM USE ONLY							
Staff Initials: _____							
Date Dispensed: _____				Date Returned: _____			
# pills/caps/tabs dispensed: _____				# pills/caps/tabs returned: _____			

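### The aluminum-antacid rule that protects the tetracycline label is missing from the matching demeclocycline instructions, and no reason is given

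*Combined protocol and SAP*

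**What the plan says.** **Tetracycline (second label set, before surgery).** Section 7.1.8 asks patients "not to take aluminum containing antacids two hours before and after the medication has been given as it can interfere with bone binding". The Cycle 2 schedule and the Cycle 2 diary in Appendix 2 repeat the two-hour restriction in patient language. The summary in section 5.2.2 does not; on timing it says only "Tetracycline should be administered on an empty stomach: 1 hour prior to meals, or 2 hours after meals".

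**Demeclocycline (first label set, before radiotherapy).** Antacids are not mentioned in any of these places:
- Section 5.2.1: "Demeclocycline should be administered 1 hour before or 2 hours after food or milk, with adequate amounts of fluid".
- Section 7.2.8 gives the same food and milk timing, then "Administer with adequate amounts of fluid to decrease the risk of esophageal irritation and ulceration", then the limit of three consecutive days.
- Cycle 1 schedule: "You should take the dose with an adequate amount of fluids to reduce throat irritation".
- Cycle 1 diary: "Please take your dose 1 hour before or 2 hours after food or milk", with a glass of water and the three-day limit.

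**How the two drugs are related.** Section 2.3.2 says of demeclocycline "It is a tetracycline derivative, and has a similar safety profile", and that "it will be used as an accessory fluorescent label (in addition to tetracycline) for dynamic histomorphometry studies". Section 8.3.8 describes both sets as tetracycline double labels that differ in color. Sections 2.4.3 and 8.3.8 give the main advantage of the scheme as letting each patient act as their own pre-treatment reference.

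**The concern.** The protocol's stated reason for the antacid rule is bone binding, and binding to bone is the job both drugs do here. Yet a surgical-arm patient who follows the paper instructions exactly is warned off aluminum antacids around the second label set and not around the first. The first set is the pre-radiation reference. If the interaction applies to both drugs, the two halves of the within-patient comparison are collected under different protection.

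At stake are the dynamic measures in objective 1.3.3: mineral apposition rate, mineral formation rate and mineralization lag time. The labels are read in bone taken at surgery (section 8.3.3), so a poor pre-radiation label cannot be repeated once it is seen there.

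**Working it through.** No power, alpha or effect size enters this point, and the plan states no figure to reproduce. The check is a side-by-side reading of every visible dosing instruction.

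| Level of text | Tetracycline | Rule present? | Demeclocycline | Rule present? |
|---|---|---|---|---|
| Short summary | 5.2.2 | No | 5.2.1 | No |
| Administration section | 7.1.8 | Yes, with reason | 7.2.8 | No |
| Patient schedule | Cycle 2 | Yes | Cycle 1 | No |
| Patient diary | Cycle 2 | Yes | Cycle 1 | No |

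1. **Contrast.** The summaries treat the two drugs alike, so they are not evidence of a difference. Among the matching detailed texts the rule stands in 3 of 3 for tetracycline and 0 of 3 for demeclocycline.

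2. **Does other text fill the gap?** Section 5.5 allows all concomitant therapy needed for support, without an antacid exception. Section 7.2.4 (Compatibility) is marked not applicable, as is 7.1.4 for tetracycline. The demeclocycline risk and management lists in 6.1.2 and 6.2.2 do not mention antacids. The wording of 7.1.8 refers generically to the medication, but it sits under tetracycline, and its patient-facing copies are only on the Cycle 2 sheets. No visible text explains the difference.

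3. **Would antacid use be detected?** The Cycle 1 diary has a log of other medications, prescribed or not, with dates taken, and patients bring the diary to the next visit. It may therefore reveal antacid use before surgery. It does not prevent that use. It also records dates rather than times for other medications, so it cannot show whether an antacid fell within two hours of a dose.

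4. **Doses without the instruction.** 3 days × 4 doses = 12 doses per label; 12 × 2 labeling periods = 24 per set; 24 × 2 sets = 48 per surgical patient. The instruction is missing for 24 of 48 doses, taken on 3 × 2 = 6 days. This counts doses lacking the sentence, not doses known to be at risk.

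5. **Which analyses are touched?** The primary endpoint is trabecular density by QCT, which does not use the labels. Section 14.2 compares iliac crest with sacrum. Both sites receive the same swallowed doses, so that comparison is largely unaffected. Section 14 names no test of pre- against post-radiation labels. What remains is the dynamic histomorphometry, a secondary objective in 1.3.3 listed as exploratory in 14.1.2.

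**The case against.** The strongest reply is that the documents never say that aluminum antacids affect demeclocycline. The sentence in 2.3.2 that links the drugs is about safety, not binding. Section 7 also gives them different properties: tetracycline is not metabolized and has a half-life of 6-11 hours, while demeclocycline has hepatic metabolism and a half-life of 10-17 hours. The instructions differ in the other direction too, since the demeclocycline texts mention milk and fluids and the detailed tetracycline text does not. That fits instructions written separately for each drug, and protocols rarely justify what they leave out.

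This stands in part. The interaction is an inference, and intent cannot be read from the text. It does not remove the point, because the reason given in 7.1.8 concerns the shared function of the two drugs and 8.3.8 treats both as tetracycline labels. The question to pharmacy is therefore fair, and either answer improves the protocol.

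A reader might go further and infer that an antacid taken near a dose would make a label unreadable and cost that patient the pre-radiation value, since apposition rate in 2.4.3 is the distance between two consecutive labels. The documents do not support this. Each label is built from 12 doses over three days, and nothing says that an antacid near some of them erases it. Nor can it be said that a problem would surface only in the biopsy, because the diary log may show antacid use earlier.

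**Conclusion.** The inconsistency is real but minor. In the visible text, the antacid rule covers the post-radiation label in all three detailed places and the pre-radiation label in none, without explanation. The pre-radiation label may therefore be less well protected.

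This rests on one assumption the documents do not confirm: that the binding concern in 7.1.8 extends to demeclocycline. They give no rate of antacid use and no size of interaction, so the loss of label cannot be derived, and it could be nil.

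The scope is the dynamic histomorphometry in the planned 20 surgical patients. A reader might infer a threat to the primary result or to the power calculation; neither depends on the labels. Figure 12 and the consent pages were not visible, so antacid advice given there would narrow the gap.

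**What to change.** Ask pharmacy whether the aluminum-antacid restriction applies to demeclocycline. Unless it is found exempt, add the 7.1.8 sentence to section 7.2.8, the Cycle 1 schedule and the Cycle 1 diary, and to sections 5.2.1 and 5.2.2 so that the summaries agree: 3 + 2 = 5 places. If demeclocycline is exempt, say so in 7.2.8.

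No new data, visits or procedures are needed. The cost is a minor amendment, which section 13.1 requires the IRB to approve before use, slightly longer patient sheets, and a two-hour antacid restriction around doses on six days. Cycle 2 already asks the same of patients.
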